PARTNERS HUMAN RESEARCH COMMITTEE PROTOCOL SUMMARY

Answer all questions accurately and completely in order to provide the PHRC with the relevant information to assess the risk-benefit ratio for the study. Do not leave sections blank.

PRINCIPAL/OVERALL INVESTIGATOR

[name]

PROTOCOL TITLE

Robotic-assisted therapy to improve manual dexterity in children with cerebral palsy: a pilot study on clinical outcomes and muscle synergies as a possible predictor of response.

FUNDING

Thrasher Research Fund

VERSION DATE

August 3rd, 2020

SPECIFIC AIMS

Concisely state the objectives of the study and the hypothesis being tested.

Aim 1. Assess the effectiveness of robot-assisted training on hand function and quality of life in children with CP.

Aim 2. To study the relationship between muscle synergies and the outcomes of robot-assisted training.

BACKGROUND AND SIGNIFICANCE

Provide a brief paragraph summarizing prior experience important for understanding the proposed study and procedures.

Pediatric cerebral palsy (CP) is a group of disorders affecting movement, development and posture leading to functional limitations. CP is the most common motor disorder in children (over 2 per 1 000 live births¹) and the leading cause of chronic childhood disability. It is attributed to non-progressive alterations occurring in the brain during fetal and newborn development². Clinical features of children with CP usually include weakness, spasticity, and loss of selective motor control³. Often, there are deficits in the integrity of neuroanatomical structures and pathways required for precision grasping and fine motor control of the fingers^{4,5}. As such, skilled finger movements and hand function do not develop normally⁶⁻⁸. This leads to severe limitations in activities of daily living (ADL)⁹⁻¹¹. The severity of impairments observed in children with CP is associated with deficits in specific domains of quality of life (QoL) (*i.e.* physical well-being, and social support and peers)⁹. Also, overall participation in ADL also has a significant impact on QoL (*i.e.* physical well-being, moods and emotions, and social support and peers)⁹. Therefore, not only should therapy focus on improving motor symptoms, it should aim to improve the performance of ADL.

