Based on motor learning theories, recent studies have demonstrated that **intensive, repetitive, task-oriented therapies** (IRTT) can help a paretic limb “relearn” how to perform movements that were lost after brain damage^{12,13}. The same principle can be applied to children with CP that do not have to relearn given movements but rather learn how to perform them in a functionally adequate manner¹⁴⁻¹⁶. The mechanism by which functional recovery and motor learning are believed to occur is through the enhancement of neuronal plasticity¹⁷. A motor learning study in humans has shown that 300 to 800 repetitions per session are needed for motor learning to occur¹⁸ yet, only an average of 32 repetitions of upper-limb movements is achieved during conventional therapy¹⁹. There is robust evidence that IRTT can improve motor and functional ability of the hand²⁰. While there is limited evidence for the efficacy of most approaches to hand rehabilitation in CP²¹, some studies have demonstrated that children with hemiplegia may benefit from intensive unimanual practice^{14,15}. One approach that has demonstrated promising outcomes in hand rehabilitation in children with CP is constraint-induced movement therapy (CIMT)²²⁻²⁷ since it involves restraining the non-paretic limb while providing intensive targeted practice with the paretic limb. However, the use of CIMT is fundamentally flawed when done in children²⁸ and, as such, must be modified; and the approach can lead to temporary deficits in QoL during the prolonged treatment period (use of a cast). Consequently, novel approaches that enable IRTT need to be implemented in children with CP. Robotic devices have become a very important area of research because of their capacity to achieve IRTT^{29,30}. While the use of robotic-assisted therapy (RAT) to improve grasping and fine motor control has yet to be implemented in children with CP, RAT has been demonstrated as an effective intervention in children with CP for gait rehabilitation³¹⁻³⁷ and reaching movements^{38,39} suggesting that using the RAT could improve hand function in this population. In the proposed study, we will assess the effectiveness of the Amadeo®. The device has been shown to improve manual dexterity in stroke survivors. The computer-controlled device maintains patients’ forearm in a secure position using Velcro straps. The patients fingertips are then attached to the robotic device using mild adhesive tape (like a band aid). Patients then have to control interactive games displayed on the screen using their fingers.

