
In addition to assessing the efficacy of RAT, the proposed study aims to identify predictors of responsiveness to the intervention. This is of significance in order to adequately select children that will obtain the best outcome following IRTT as much variability can be observed in response to RAT. Baseline functional impairments have been shown to be important determinants of overall gross motor improvements following RAT of gait (*i.e.* more initial impairment → less improvements) suggesting that children may need to attain a certain level of motor function before being able to achieve optimal outcomes using RAT. While the current study also proposes to identify predictors of motor outcome following RAT using clinical outcome measures, we will also utilize a physiological measure (muscle synergies) that we have assessed to be a predictor of motor outcome following RAT of gait.

The scientific community widely accepts that the Central Nervous System (CNS) adopts several strategies to reduce the complexity of the control of movement⁴⁰⁻⁴⁴. Many authors have shown that one of these strategies consists in using a limited number of primitive signals undergoing the activation of muscles which, when combined, generate a full collection of movements⁴¹.

Some studies have shown that the sensitive nature of EMG to represent an aberrant motor control in CP⁴⁵. However, the assessment of muscle synergies during grasp has yet to be performed in this or any other population. Nonetheless, the similarity of gait synergies in CP, stroke, and

infant rhythmic-stepping indicates that there are common changes in control after brain injury that may reflect control in early development⁴⁶.

Whereas clinical measures of impairment in SMC are available⁴⁷, such measures do not provide information that is suitable to design physical therapy interventions aimed to address specific impairments and hence improve clinical outcomes of robot-assisted gait training.

If successful, the proposed approach would be expected to significantly improve clinical outcomes of manual dexterity in children with CP.

RESEARCH DESIGN AND METHODS

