Briefly describe study design and anticipated enrollment, i.e., number of subjects to be enrolled by researchers study-wide and by Partners researchers. Provide a brief summary of the eligibility criteria (for example, age range, gender, medical condition). Include any local site restrictions, for example, “Enrollment at Partners will be limited to adults although the sponsor’s protocol is open to both children and adults.”

A sample of 10 children with CP with no major orthopedic or neurological complications that could interfere with the robot-assisted training will be recruited in the study. This sample size was calculated for an F test with an effect size of 0.4, an alpha of 0.05, a beta of 0.80, a correlation coefficient between repeated measures of 0.7, and an attrition rate of 20%. A study clinician will screen potential subjects. Screening will include a standard history and physical exam to ensure subjects meet all entry requirements after consideration of inclusion and exclusion criteria. Specifically, [name], the study physician, will assess all subjects' suitability for using the Amadeo.

Inclusion criteria:

- Diagnosis of CP with upper-limb impairment
- 6 to 18 years of age.
- Manual Ability Classification Scale Level II or III.
- Ability to communicate pain or discomfort.

Exclusion Criteria:

- Recent use of upper-limb robotic-assisted training within the last 3 months.
- Contraindication to robotic-assisted manual training such acute and pronounced pain symptoms despite conventional pain therapy of the upper-limb, lack of compliance, high-grade ataxia, advanced osteoporosis, and fractures of the upper-limb.
- Modified Ashworth Scale (MAS) of 4 in the upper-limb.

Briefly describe study procedures. Include any local site restrictions, for example, “Subjects enrolled at Partners will not participate in the pharmacokinetic portion of the study.” Describe study endpoints.

All study procedures will take place in the Motion Analysis Laboratory at Spaulding Rehabilitation Hospital, Boston, Massachusetts, USA. Spaulding Rehabilitation Hospital is an affiliated hospital of Harvard Medical School.

Assessments

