Once the children are enrolled in the study, they will undergo a baseline assessment before undertaking a 6 weeks/18 sessions RAT program. Once training is completed, the children will undergo a final assessment. Finally, a follow-up assessment will be performed one month after the end of the RAT program to evaluate retention in the quality of life.

The follow up assessment will be performed 4 weeks after the end of the intervention and will consist in the cerebral palsy Quality of Life Questionnaire, which it will be provided to the subjects and they will be asked to fill it out and return to us when completed by email or mail (note: the questionnaire does not include any identifiable information).

Clinical tests

Clinical tests will be conducted by a study staff before and after the intervention. Clinical testing should last about 1 hour and will include:

- Physical examination: we will gather measures of Range of Motion (ROM) and muscular strength for the upper extremities. Passive and active movements of the shoulder (flexion, extension, abduction and adduction), elbow (flexion and extension), radioulnar joint (pronation and supination), wrist (flexion, extension, abduction, and adduction), and fingers (flexion, extension, abduction, and adduction) will be assessed with a goniometer.
- Modified Ashworth Scale (MAS)^{48,49}: We will assess spasticity at the shoulder (flexion-extension); elbow (flexion-extension); radioulnar (pronation-supination), and wrist (flexion-extension).
- Quality of Upper Extremity Skills Test (QUEST): this standardized test is a validated and reliable tool to evaluate movement patterns and hand function in children with cerebral palsy. The QUEST evaluates quality of upper extremity function in four domains: dissociated movement, grasp, protective extension, and weight bearing.
- Box and block test⁵²: this test assesses unilateral gross manual dexterity. Children are seated at a table, facing a rectangular box that is divided into two square compartments. The individual is instructed to move as many blocks as possible, one at a time, from one compartment to the other for a period of 60 seconds.

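### Aim 1 claims effectiveness, but one trained group of 10 children with no comparator can only estimate change after training, and changes in other therapy between assessments are not recorded

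*Combined protocol and SAP*

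**What the plan says.** **The goal.** Specific Aims gives Aim 1 as "Assess the effectiveness of robot-assisted training on hand function and quality of life in children with CP". Background and Significance says "In the proposed study, we will assess the effectiveness of the Amadeo" and later "In addition to assessing the efficacy of RAT, the proposed study aims to identify predictors of responsiveness to the intervention". The title is more cautious: "a pilot study on clinical outcomes and muscle synergies as a possible predictor of response".

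**The design.** Research Design and Methods plans "A sample of 10 children with CP with no major orthopedic or neurological complications". Under Assessments, once enrolled, "they will undergo a baseline assessment before undertaking a 6 weeks/18 sessions RAT program", followed by a final assessment. Hand function is tested before and after training only. The quality-of-life questionnaire is repeated 4 weeks after training ends. The clinical analysis is descriptive, pre against post. For Aim 2, changes in synergies and in QUEST and Box and Block scores are examined child by child.

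**Other therapy.** The only rule is an entry exclusion: "Recent use of upper-limb robotic-assisted training within the last 3 months". The standard-of-care paragraph lists other treatments for manual dexterity and spasticity, and describes the robot training as an advanced form of intensive unimanual physical therapy.

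**The concern.** Effectiveness and efficacy are causal claims: they mean change beyond what would have happened without the robot. With every child trained and no comparator, a change could also reflect practice on the tests, maturation, regression to the mean, other therapy, or the expectations of whoever scores the tests. The design gives no means of separating these from an effect of training.

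The aim governs what the report may conclude. As worded, an improvement from before to after could be reported as effectiveness of the robot. The wording also has a later use, because Background and Significance and Expected Benefits both look ahead to selecting children who will respond.

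Other therapy deserves separate mention because it is the one rival explanation that the trial could document at little cost. If a treatment starts, stops or changes during the study and nobody notes it, the result can move in either direction and the reason is lost. This matters most for Aim 2, where results are read one child at a time.

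**Working it through.** **1. The plan's own figure.** The sample size of 10 is stated for an F test with effect size 0.4, alpha 0.05, a beta of 0.80 (read here as power), correlation 0.7 between repeated measures and 20% attrition. I read it as a one-group, within-child test with 0.4 as Cohen's f and sphericity assumed. The noncentrality is f² × n × m / (1 − ρ), with m measurements and degrees of freedom m − 1 and (n − 1)(m − 1).

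- m = 3, n = 7: 0.16 × 7 × 3 / 0.3 = 11.2; power 0.753.
- m = 3, n = 8: 0.16 × 8 × 3 / 0.3 = 12.8; power 0.825.
- Allowing for attrition: 8 / 0.80 = 10, which matches the plan.

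So the stated figure reproduces as a test of change over time within children. Its power concerns whether scores change, not why, so it does not support an effectiveness claim. (The match needs three measurements, while hand function is measured twice; that is a separate matter.)

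**2. Goal against design.**

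| Needed to assess effectiveness | What the protocol provides |
|---|---|
| A comparison with no robot training | None: no control group, randomisation, waiting period, repeated baseline or historical comparator |
| An analysis of that comparison | A descriptive pre/post comparison in one group |

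The between-limb comparison in the lab-based study concerns muscle synergies and is not a control for Aim 1.

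**3. Where therapy might be captured.**

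- Eligibility: the robotic-training exclusion, at entry only.
- Screening: a standard history and physical examination, which may capture some baseline therapy.
- Privacy and Confidentiality: intake interview forms are mentioned without their content; these may also capture some.
- Safety section: screening continues during enrolment, but for medical conditions that contraindicate participation.

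No section describes recording changes in therapy between assessments.

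**4. Length of the interval.** Inputs: 18 sessions, up to 4 per week, over up to 7 weeks (Training); nominally 6 weeks (Assessments); follow-up 4 weeks after training (Assessments).

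- Shortest permitted training: 18 / 4 = 4.5 weeks. Longest: 7 weeks.
- Hand function, pre to post: about 4.5 to 7 weeks.
- Quality of life, baseline to follow-up: 4.5 + 4 = 8.5 to 7 + 4 = 11 weeks.

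The gaps between each assessment and the nearest training session are not stated, so these are approximate. They are periods in which a therapy change could occur, not estimates of bias.

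**5. Consequence for Aim 2.** The clinical scores used there are QUEST and Box and Block. A therapy change in one child could alter that child's change on either score, and a case-by-case reading has no averaging to dilute it.

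**The case against.** The title calls the study a pilot and speaks only of a possible predictor, Aim 2 asks only about a relationship, and the clinical analysis is descriptive. The document is also a protocol summary that asks for brief answers, so missing form-level detail is weak evidence that nothing is recorded. This has some force. It does not remove the mismatch, because Specific Aims and Background and Significance still name effectiveness and efficacy as goals, and the sample size is justified by an F test.

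A reader might infer more than the document supports:

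- **That the assessors are unmasked.** The protocol says only that study staff conduct the tests, and it plans video recording with permission, so masked rating is not ruled out. All one can say is that no masking is described.
- **That no therapy history is taken.** The screening history and intake forms may capture some at baseline. The gap is in changes afterwards.
- **That many children will be in active treatment.** Referral by attending physicians and flyers in therapy gyms make this plausible, but they are among ten recruitment routes and no number is given.
- **That the period at risk is longer.** Adding the 3-month period from the robotic-training exclusion would lengthen it, but nothing shows that this period suits the other therapies.
- **That the title and the response-to-therapy heading must change.** The text under that heading already works with differences between visits, so rewording there is a matter of preference.
- **That spasticity or quality-of-life scores drive Aim 2.** They are not among the clinical scores named for that analysis.

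**Conclusion.** The concern holds in a limited form. Aim 1 and two sentences in Background and Significance promise something that a single group with a descriptive pre/post comparison cannot deliver. That the study has one arm is inferred from the design; the term itself is not used. Separately, no recording of therapy changes is described over about 4.5 to 7 weeks for hand function and 8.5 to 11 weeks for quality of life, assuming that the permitted session frequency and duration are applied as written.

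The size and direction of any resulting bias cannot be derived from the document. A reader might infer that an observed improvement would be spurious, or that the pilot needs a control arm; neither follows. The study can run as designed, provided its aim and conclusions are confined to change after training. The change should be made because the mismatch affects what may be concluded and costs little to correct.

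**What to change.** 1. **Wording.** Restate Aim 1 as: *Estimate the change in hand function and quality of life after robot-assisted training in children with CP*. Align the effectiveness and efficacy sentences in Background and Significance. Add that, without a comparator, change will not be attributed to the robot. The title and the response-to-therapy heading may stay, with response understood as pre/post change.
2. **Therapy log.** On a form coded by study number, record at baseline any current therapy of the kinds listed in the standard-of-care paragraph. Record any start, stop or change, with dates, at the existing training sessions, the final assessment and the follow-up contact. Using the sessions avoids relying on recall at the final visit. List and flag affected children in the individual and case-by-case results, descriptively only. No restriction on other care is proposed.
3. **Limitations.** State that there is no comparator and that no masking of assessors is described. The log reduces ambiguity but does not permit attribution.

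**Cost.** A little staff and family time, ethics review of the wording and form, and a more modest stated aim. The follow-up questionnaire is described as carrying no identifiable information, so adding a coded form with dates to that contact must be checked against that statement. No visit is added.

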- The cerebral palsy Quality of Life Questionnaire⁵³: this standardized test assesses 7 domains related to quality of life (social wellbeing and acceptance, feelings about functioning, participation and physical health, emotional wellbeing and self-esteem, access to service, pain and impact of disability, and family health) and was specifically developed for children between 4-12 years of age with cerebral palsy. It is designed for self- and parent proxy report.
- *Statistical analyses*: We will perform a descriptive analysis of the different outcome measures and compare results between pre and post intervention.

Lab-based study

We propose to analyze the muscle synergies of subjects using a method developed by members of the Motion Analysis Laboratory and their collaborators^{41,54-60}. Subjects will be asked to reach and grasp objects of different sizes and shapes. Electromyographic (EMG) activity will be collected from 16 muscles of the upper-limb (*i.e.* Teres Major, Infraspinatus, Superior trapezius, Deltoid anterior/posterior, clavicular head of Pectoralis major, Triceps brachii lateral head, Biceps brachii (long head), Brachioradialis, Extensor digitorum communis, Extensor carpi radialis longus, Flexor carpi radialis, Flexor carpi ulnaris, First dorsal interosseous, Abductor pollicis brevis, Abductor digiti minimi). This same procedure will be replicated contralaterally. Additionally, reflective markers will be placed bilaterally on the subjects' upper-limbs (*i.e.* C7, T10, Manubrium sterni, Xiphoid process, Acromion, Lateral epicondyle, Styloid process of the radius, Styloid process of the ulna, distal head of the first/second/third/fourth/fifth metacarpus, distal head of the first/second/third/fourth/fifth proximal and distal phalanges, and distal head of the second/third/fourth/fifth middle phalange) in order to assess movement kinematics. The entire process should last approximately 1.5 hour.

Extracting Muscle Synergies: Muscle synergies and their activation coefficients will be extracted from the EMGs using a nonnegative matrix factorization (NMF) algorithm. The NMF models the activity of the muscles as a linear combination of several muscle synergies, each activated by a time-dependent coefficient. Synergies will be extracted separately from the EMGs of each limb. A first estimate of the number of synergies of each limb will be obtained based the quality of reconstruction of the original EMG channels.

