Estimating the Number of Muscle Synergies: We will decompose the EMG matrix increasing the number of synergies up to the point where the reconstructed envelopes, obtained multiplying the synergy vectors by the temporal activations, have an average R^2 similarity with the EMG envelopes above 0.8 and a minimum R^2 similarity on the individual channel above 0.6.

Quantifying Synergy Similarity: Similarity between the synergies of each limb will first be assessed using the scalar product. We will further quantify synergy similarity by estimating the dimensionality of the subspace shared between the spaces spanned by the synergies of the two limbs by computing the principal angles between sets of synergy vectors and finding the number of principal angles whose cosines are greater than a threshold.

Statistical analyses: Results of the number of synergies, and similarity between limbs will be compared descriptively.

Assessing the relationship between muscle synergies and response to therapy: The relationship between changes in the Muscle Synergies and clinical scores (QUEST and Box and Block Test) will be investigated on a case by case basis evaluating the differences between the visits.

We will ask permission to study participants to video record them during the performance of the above-described clinical tests and the lab-based study.

Training:

Training will be performed using the Amadeo®. The computer-controlled device maintains patients' forearm in a secure position using Velcro straps. The patients fingertips are then

attached to the robotic device using mild adhesive tape (like a band aid). Patients then have to control interactive games displayed on the screen using their fingers.

- Each training session will include 30 minutes of active movements that can be divided into up to 3 bouts of 10 minutes depending on patient fatigue. During the training bouts, children will be encouraged to move continuously and as actively as possible. The Amadeo® provides several interactive games to facilitate motor learning. Between bouts, children will be allowed to rest for at least 5 minutes. Adjustments in training intensity will vary according to the children's ability and endurance. Training will take place up to 4 times per week for a total of 18 sessions over up to 7 weeks. Sessions will last approximately 60 minutes (including setup, training, and rest between each bout).

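### The R² cut-off that sets the number of synergies can change that number, and the shared dimension, between recordings when the synergies themselves have not changed

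*Combined protocol and SAP*

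**What the plan says.** Everything relevant is in the protocol's *Lab-based study* section. EMG "activity will be collected from 16 muscles of the upper-limb", and the recording is repeated on the other side.

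- *Extracting Muscle Synergies*: "Synergies will be extracted separately from the EMGs of each limb". On how many there are: "A first estimate of the number of synergies of each limb will be obtained based the quality of reconstruction of the original EMG channels". No later refinement step is described.
- *Estimating the Number of Muscle Synergies*: the number is raised until the reconstructed envelopes "have an average R^2 similarity with the EMG envelopes above 0.8 and a minimum R^2 similarity on the individual channel above 0.6"; both conditions must hold.
- *Quantifying Synergy Similarity*: similarity between limbs is assessed first by the scalar product, then by "finding the number of principal angles whose cosines are greater than a threshold". The threshold is not given.
- *Statistical analyses*: "Results of the number of synergies, and similarity between limbs will be compared descriptively"; no test is planned.
- *Assessing the relationship between muscle synergies and response to therapy*: the link between changes in the synergies and changes in QUEST and Box and Block scores "will be investigated on a case by case basis evaluating the differences between the visits".

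The documents do not say whether the number is chosen afresh at each visit. They give no rule for rejecting a poor channel, no definition of R² (centred or uncentred), no test-retest error and no sensitivity analysis on the number.

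**The concern.** The number of synergies is a small integer produced by two hard limits, one of which depends only on the worst-fitting channel. A recording close to either limit can fall on one side at one visit and on the other side at the next. The shared dimension is computed from sets of synergies whose sizes were chosen this way, so it inherits the instability.

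Aim 2 and the study title treat synergies as a possible predictor of response. With 10 children planned (8 if the assumed 20% attrition occurs: 10 × 0.8) and each read individually, there is no averaging and no error term. A one-synergy change caused by noise would look the same as a real one, and so would a real change masked by noise.

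**Working it through.** **Plan's own figure.** The limits 0.8 and 0.6 are design choices without a derivation, so there is no calculation to reproduce. The inputs from the protocol are 16 channels, the two limits, extraction per limb, and comparison between visits.

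**Step 1: can one channel set the number?** With 16 channels, mean R² = (15a + b)/16.
- a = 0.90, b = 0.55: (13.50 + 0.55)/16 = 0.878. The mean passes 0.8 but the floor fails, so a synergy is added.
- a = 0.82, b = 0.59: (12.30 + 0.59)/16 = 0.806. The same happens.

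If noise is a share v of a channel's variance, a perfect fit to the signal gives centred R² of about 1 − v. At v = 0.5 or 0.7 that is 0.5 or 0.3, below the floor, so the rule can be met only by fitting noise. At v = 0.05 or 0.15 it is 0.95 or 0.85.

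**Step 2: does the shared dimension follow?** Two sets of p and q synergies have min(p, q) principal angles, so the count cannot exceed min(p, q). If the limbs go from (4, 4) to (4, 3), the largest possible count falls from 4 to 3, whatever the true overlap.

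**Step 3: how often?** The rule was applied by NMF to simulated non-negative envelopes with 16 channels and the same true synergy vectors at both recordings. Noise levels and activation patterns are assumptions.

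| Set | Assumptions | Number differs, ordinary noise | Number differs, one poor channel |
|---|---|---|---|
| A | 4 synergies, 500 samples, noise SD 0.2–0.45 of signal SD, 200 pairs | 34.5% | 67% (noise SD equal to signal SD; mean shift +0.78) |
| B | 5 synergies, 12 trials, noise 5% or 15% of variance, same activations, centred and uncentred R², 60 pairs per cell | 15–30% | 20–37% (50% noise); 37–67% (70% noise) |
| C | 4 synergies, activations redrawn, 80 runs | 51% | 70% |
| D | 4 synergies, 500 samples, noise SD 0.2–0.45 of signal SD, other activation shapes and loadings, 120 pairs | 40–67% by batch | not reported |

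Ordinary noise alone therefore gives roughly 15–67%. For one limb in 10 children, that is 1.5 to 6.7 children with a spurious change.

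In set A, dropping the poor channel from both recordings cut the mean shift to +0.04, but the number still differed in 37.5% of pairs. In set B with no poor channel, the floor rather than the mean fixed the second-visit number in 48–82% of runs. Using the mean condition alone, the number differed in 2–10% of pairs instead of 15–30%.

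**Step 4: shared dimension (set B, cosine thresholds 0.8 and 0.9 assumed).** Share of unchanged pairs in which it changed:

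| | Protocol's rule | Common number 5, no channel screening |
|---|---|---|
| No poor channel | 22–32% | 5–13% |
| One channel at 50% noise | 22–33% | 15–28% |
| One channel at 70% noise | 25–35% | 55–75% |

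**Step 5: largest rule-based number per child, with the poor channel dropped (cosine 0.9 assumed).** In set C, spurious change in shared dimension fell from 48% to 21% with ordinary noise and from 69% to 26% with a poor channel. In a further set of 60 runs it fell from 38% to 2%, with or without a poor channel.

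**The case against.** **Selection at each visit is not written.** A reader might infer that the plan expressly re-chooses the number at every visit. It does not say so; only selection per limb is explicit, and the number is called a first estimate. But a between-visit change in the number can exist only if it is estimated at each visit. If the intention is to hold it fixed, the plan needs to say so, and selection per limb would still affect the comparison between limbs.

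**One noisy channel is not the main cause.** The arithmetic in step 1 makes that reading tempting. Set A still shows 37.5% of pairs differing after the poor channel is removed, and in set B a poor channel adds little to the instability of the shared dimension. Ordinary noise at the cut-off is enough.

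**A common number is not a cure.** In set A, fixing the number at the simulated truth recovered the shared dimension every time, but no analyst knows the true number. In set D, with no poor channel, the shared dimension was read correctly in about 27% of pairs under the rule, 59% with the largest rule-based number and 70% even at the true number. With a poor channel left in, these were about 36%, 41% and 49%, and the largest number carried the noisiest recording's inflation into the others. This objection stands, and it is why screening and a sensitivity analysis belong in the fix.

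**The study is a small descriptive pilot with limits set in advance.** This is true. No test, error rate or clinical decision depends on these measures. The scalar-product similarity is not an integer count and was not tested here.

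**Conclusion.** The concern holds in a limited form. Under the rule as written, the number of synergies and the shared dimension can differ between recordings with unchanged synergies, and nothing in the plan would reveal it. The step 1 arithmetic and the cap on the principal-angle count need no simulation. The rate of roughly 15–67% from ordinary noise rests on assumed noise, activation patterns and numbers of true synergies, and should be read as showing that the effect is not negligible, not as an estimate for this laboratory. The shared-dimension figures also rest on an assumed cosine threshold.

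A reader might infer that Aim 2 is invalid or that a type I error rate is inflated. The documents support neither: the analysis is descriptive, and the scalar-product measure was not examined. What is at stake is how individual children's changes are interpreted. That justifies a change to the analysis text but is no bar to running the study.

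**What to change.** In *Estimating the Number of Muscle Synergies* and the paragraphs that follow it:

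1. Before factorization, apply a channel-quality criterion fixed in advance, and drop a failing channel from all of that child's recordings (both limbs, both visits). A common number without this step does not protect against a poor channel.
2. Keep the rule-based number per recording as a description.
3. Base between-visit and between-limb comparisons on one common number per child across both limbs and visits, for example the largest that the rule gives after screening. Repeat them at neighbouring numbers as a sensitivity analysis.
4. Report mean R², similarity and shared dimension at that common number. State the R² definition and the cosine threshold.
5. Show each child's between-visit change beside the spread from resampling reach-and-grasp trials within a visit.

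The cost is a few sentences and a little more analysis of data already collected. There are two downsides: a true change in the number would appear as a change in R² rather than as an integer, and a failed channel is lost from all of that child's recordings.
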